# 6.7.2 Tumor Lysis Syndrome (TLS)

Blood chemistry (creatinine, potassium, calcium, magnesium, phosphorus, and uric acid) will be monitored every 8 hours for 72 hours after start of infusion to monitor for tumor lysis. If it occurs, appropriate treatment will be initiated that will include correction of serum calcium, potassium, or phosphorus abnormalities, and treatment of hyperuricemia with allopurinol and/or rasburicase, as indicated in Appendix J (35).

# 6.7.3 Hematological adverse events

Patients will receive packed red blood cells and platelet transfusions to manage anemia and thrombocytopenia, if needed. In addition, G-CSF may be administered to patients with neutropenia, except in Cycle 1 of the Dose Escalation Part. Antibiotics will be provided to patients with febrile neutropenia, in accordance with local practice. Details on the management of hematological toxicity are provided in Section 6.5.4.

# 6.7.4 Other adverse events

Other toxicities must be managed as clinically indicated. Details on dose delay and modification of dosing for patients with other toxicities are provided in Section 6.5.5.

# 6.7.5 Initiation of a new cycle of therapy

In the Dose Escalation Part, at the end of Cycle 1, 43 days after the first SAR440234 infusion, a patient may begin Cycle 2 if he or she did not experience a DLT. Details on the start of the next infusions are provided in Section 6.5.

In the Dose Escalation Part Cycle 2 and beyond, and for the Expansion Part Cycle 1 and beyond, details on the start of the next infusions are provided in Section 6.5.

Property of the Sanofi Group - strictly confidential

Page 68

### 6.8 DURATION OF STUDY PARTICIPATION

# 6.8.1 Duration of study participation for each patient

The duration of the study for a patient will include a period for screening of up to 14 days starting from the time the patient signs the informed consent form. The cycle duration is 42 days with weekly IMP administration (except for Cycle 1 Week 1 in DL ≥3 when 2 administrations will be given). After study treatment discontinuation, patients will return to the study site 30 days after the last IMP administration for end of treatment assessments. If a patient discontinues SAR440234 prior to day 42, the day 42 evaluation must be performed on the day that the decision is made that the patient will not continue treatment with SAR440234. EOT evaluation for a patient must be performed within 30 days of the last administration of SAR440234 received by the patient. If a patient does not plan to return to the study site for an EOT visit, the EOT evaluation must be performed on the day that the decision is made that the patient will not continue treatment with SAR440234.

Patients may continue treatment with the IMP as long as clinical benefit is possible, or until disease progression, unacceptable adverse reaction, patient's decision to stop treatment, or other reason for discontinuation. During the follow-up period, IMP-related AEs and all serious adverse events (SAEs) (regardless of relationship to study treatment) present at the time of study treatment discontinuation will be followed every month until resolution or stabilization, or until initiation of another antineoplastic therapy. If a patient is unable to attend monthly follow-up visits, the investigator will obtain follow up information via telephone call and record review from the treating physicians.

Clinical benefit is defined as: CR, CRi, PR, reduction of blast count, stabilization of symptoms and conditions, or any other clinical benefit identified and documented by the Investigator.

Patients without documented disease progression at the end of a treatment visit who have not yet started treatment with another anti-cancer therapy will proceed with monthly follow-up visits until initiation of another anti-cancer therapy, disease progression, study cut-off date, or death, whichever comes first. If a patient is unable to attend monthly follow-up visits, the investigator will obtain follow up information via telephone call and record review from the treating physicians.

The first cut-off date will be at the end of the first cycle of the last patient treated in the Dose Escalation Part in order to have at least the first cycle evaluable for all patients for determination of the MTD and for the RP2D.

The second cut-off date will be when the last patient in the Expansion Part will have been treated for 2 cycles (approximately 3 months), or has early progression, whichever occurs first, in order to assess tumor response. After the second cut-off date, ongoing patients will receive study treatment until disease progression or occurrence of an AE leading to treatment discontinuation, whichever is earlier, and they will only be followed for study treatment administration, SAEs, study treatment-related AEs, and reason for end of treatment.

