# DURATION OF STUDY PERIOD (per patient)

The duration of the study for a patient will include a period for screening of up to 14 days. The cycle duration is 42 days. After study treatment discontinuation, patients will return to the study site 30 days after the last IMP administration for end of treatment assessments.

Patients may continue treatment with the IMP as long as clinical benefit is possible, or until disease progression, unacceptable adverse reaction, patient's decision to stop treatment, or other reason for discontinuation. During the follow-up period, IMP-related AEs and all SAEs (regardless of relationship to study treatment) present at the time of study treatment discontinuation will be followed every month until resolution or stabilization, or until initiation of another antineoplastic therapy.

[figure not shown]
Patients without documented disease progression at the end of a treatment visit who have not yet started treatment with another anti-cancer therapy will proceed with monthly follow-up visits until initiation of another anti-cancer therapy, disease progression, study cut-off date, or death, whichever comes first.

The first cut-off date will be at the end of the first cycle of the last patient treated in the Dose Escalation Part in order to have at least the first cycle evaluable for all patients for determination of the MTD and for the RP2D.

The second cut-off date will be when the last patient in the Expansion Part will have been treated for 2 cycles (approximately 3 months), or has early progression, whichever occurs first, in order to assess tumor response. After the second cut-off date, ongoing patients will receive study treatment until disease progression or occurrence of an AE leading to treatment discontinuation, whichever is earlier, and they will only be followed for study treatment administration, SAEs, study treatment-related AEs, and reason for end of treatment.

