- p Plasma cytokines (including interleukin-6 and interferon-γ): will be collected at the time points specified in the pharmacokinetic, pharmacodynamic, biomarker and immunogenicity flowcharts. An additional sample will be taken at onset of CRS Grade ≥2 if it occurs, or as soon as it is diagnosed.
- q CRP/ferritin: will be collected at the same time points as cytokines.
- r SAR440234 administration: Systematic prophylactic premedication with dexamethasone 20 mg IV 4 and 1 hour prior to infusion of SAR440234 and montelukast 10 mg oral (PO) 4 hours prior to infusion are required. Dexamethasone 20 mg IV must be repeated 5 hours after the start of infusion if CRS Grade 2 has occurred in a previous patient or previous administration in the same patient. Specific instructions for the preparation and administration of SAR440234 are provided in the Pharmacy Manual.
- s Hospitalization: Patients will be hospitalized for the duration of the SAR440234 infusion (1 to 19 hours), and for 72 hours after completion of each subsequent infusion. For DL ≥3, patients will be hospitalized continuously from Day 1 of Week 1 until 72 hours after completion of the third infusion, ie, for 11 days.
- t Adverse event assessment: The period of observation for collection of adverse events extends from the signature of the ICF until 30 days after the last administration of the SAR440234. Serious adverse events, AESIs, pregnancy, and overdose reports should be assessed and reported as described in the protocol. SAEs and ongoing treatment-related AEs should be followed beyond EOT until resolution or stabilization.
- u Concomitant medication assessment: The period of collection of concomitant medications extends from the signature of the ICF until EOT, and post EOT if associated with ongoing SAEs or ongoing treatment-related AEs.
- v The investigations and test scheduled for Day 42 may be performed on the next day if treatment continues after the current cycle; in this case the tests and investigations must be performed before start of next infusion. If the treatment won't be continued after the current cycle, all the planned tests and investigations for Day 42 must be performed on the day that the decision is made that the patient will not continue treatment.

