# 10.5.3 Follow-up

- The Investigator should take all appropriate measures to ensure the safety of the patients, notably he/she should follow up the outcome of any AEs (clinical signs, laboratory values or other, etc) until the return to normal or consolidation of the patient's condition. Ongoing related AEs at the end of study treatment will be followed until resolution or stabilization.
- In case of any SAE/AESI, the patient must be followed up until clinical recovery is complete and laboratory results have returned to normal, or until outcome has been stabilized. This may imply that follow-up may continue after the patient has discontinued study treatment or has left the clinical trial and that additional investigations may be requested by the monitoring team;
- In case of any AE or AESI brought to the attention of the Investigator at any time after the end of the study for the patient and considered by him/her to be caused by the IMP with a reasonable possibility, should be reported to the monitoring team.

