#### 12.7 PERIOD POST END OF TREATMENT

Follow up will be performed for patients with ongoing SAEs regardless of relationship to IMP and ongoing IMP-related AEs 30 days after the last IMP administration, and for patients with new IMP-related AEs/SAEs. Those events will be followed until resolution or stabilization as described in Section 10.5.3 and Section 11.1.2. Follow-up visits are to be performed monthly until initiation of another anti-cancer therapy, disease progression, study cut-off date, or death. If a patient is unable to return to clinic for monthly follow-up visits, the investigator must obtain follow up information via telephone call and record review.

29-Aug-2019 Version number: 2

Patients achieving stable disease (SD), CR, CRi, or PR or non-CR/nonprogressive disease (PD) should be followed until disease progression or initiation of another specific antitumor treatment to collect either the date of PD or the initiation of further antitumor therapy.

The Site Investigator will evaluate the patient's symptoms, physical examination, vital signs, and laboratory tests each month. If the Investigator finds evidence to indicate a change in disease status, the Investigator will obtain a bone marrow aspirate to confirm the change. If there is no perceived change in disease status, additional testing is not required.

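### The Clinical Trial Summary and Section 6.8.1 end follow-up of open SAEs and IMP-related AEs at the start of new therapy, while ten other provisions require it to resolution or stabilization

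*Protocol*

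**What the plan says.** Section 6.8.1 of the protocol covers IMP-related AEs and all SAEs that are present when study treatment stops. It says they "will be followed every month until resolution or stabilization, or until initiation of another antineoplastic therapy". The part of the Clinical Trial Summary on duration of the study period has the same rule: "until resolution or stabilization, or until initiation of another antineoplastic therapy".

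Section 10.5.3 sets a different end. For any SAE or AESI, "the patient must be followed up until clinical recovery is complete and laboratory results have returned to normal, or until outcome has been stabilized". It adds that "follow-up may continue after the patient has discontinued study treatment or has left the clinical trial". For related AEs it says: "Ongoing related AEs at the end of study treatment will be followed until resolution or stabilization".

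Section 12.7 says of open events: "Those events will be followed until resolution or stabilization as described in Section 10.5.3 and Section 11.1.2". Its next sentence concerns visits, and ends the monthly visits at another anti-cancer therapy, progression, the cut-off date or death.

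The AE footnote of flow chart 1.2.1 reads: "SAEs and ongoing treatment-related AEs should be followed beyond EOT until resolution or stabilization". The AE footnotes of flow charts 1.2.2, 1.2.3 and 1.2.4 say the same. Footnote c of flow charts 1.2.2 and 1.2.4, which is headed as covering disease status, IMP-related AEs and SAEs, ends the monthly visits at new therapy.

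**The concern.** Take a patient who stops SAR440234 with an unresolved SAE and then starts another antineoplastic therapy. Section 6.8.1 lets the site close follow-up of that event on the day the new therapy starts. Section 10.5.3 obliges the site to continue. A site that follows the first breaches the second, and two sites acting in good faith could return different data for the same kind of event.

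The trigger is foreseeable. The patients have relapsed or refractory disease, Section 8.7 leaves later treatment to the treating physician, and the protocol sets no minimum interval before new therapy.

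What is at stake is the outcome and resolution date of open events. A secondary objective is to characterize safety, including cumulative reactions. Section 6.3 asks that cumulative or irreversible toxicities be weighed in dose decisions, and irreversibility cannot be judged for an event whose follow-up was cut. DLTs and CRS are AESIs under Section 10.5.5, so they fall under the obligation in 10.5.3. The SAP (Section 4.7.2) plans a CRS listing with duration, which needs an end date.

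**Working it through.** No sample size, power or error rate is involved. The check sets side by side every protocol provision that says when follow-up of open events ends.

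| Group | Provisions | End of follow-up |
|---|---|---|
| A. Stop placed on the events | Clinical Trial Summary; 6.8.1 | Resolution or stabilization, or new antineoplastic therapy |
| B. No new-therapy stop | 9.1.2; 10.5.3; 11.1.2; 12.1; 12.7 (event sentence); 12.8; AE footnotes of flow charts 1.2.1, 1.2.2, 1.2.3, 1.2.4 | Resolution, recovery, consolidation or stabilization |
| C. Stop placed on monthly visits | 12.7 (visit sentence); footnote c of 1.2.2 and of 1.2.4 | New therapy, progression, cut-off or death |

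Count: A has 2 provisions, B has 6 sections + 4 footnotes = 10, and C has 3.

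**Can group A be read as a visit rule only?** No. Section 6.8.1 has a separate paragraph for monthly visits of patients without progression, with its own new-therapy stop. The sentence on AEs and SAEs is a further limit, attached to the events.

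**Does group C remove the conflict?** No, it widens it. In 12.7 the event rule continues while the visits end. In flow charts 1.2.2 and 1.2.4 the AE footnote continues follow-up, while footnote c, whose heading includes AEs and SAEs, ends the visits. After new therapy starts, an open event must still be followed under 10.5.3 but no contact is scheduled.

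**Does any text rank the rules?** Not expressly. Section 11.1.2 follows patients to the later of study completion and recovery or stabilization, but only for AEs that the protocol says are to be followed, which leads back to the same disagreement. Section 12.7 points to 10.5.3 and 11.1.2, not to 6.8.1.

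**What is not lost.** Section 10.5.1 requires all AEs to be recorded, with outcome, up to 30 days after the last administration, with no exception for new therapy. Detection of events in that window is not cut. The exposure is to the later course of events that are still open when new therapy starts.

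**The case against.** A reader might infer something stronger: several hematological DLTs turn on recovery within 14 days (Section 6.2.1), so new therapy inside that window could leave a DLT unclassified and, in a dose level of 3 to 6 patients, alter escalation. The documents do not support this.

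- Section 6.8.1 governs monthly tracking after discontinuation; it is not a DLT assessment rule. DLTs have their own 42-day observation period (6.2.2), an investigator assessment at the end of Cycle 1 with Study Committee review (9.1.1), and a complete safety evaluation during the DLT period (13.3.2).
- Under 10.5.1 the recording window is 30 days from the last dose. A 14-day recovery window that opens within 30 − 14 = 16 days of the last dose closes inside it.
- A patient who stops before the end of Cycle 1 for a reason other than DLT is replaced (6.3, 11.2), and a patient with a DLT but an incomplete safety evaluation stays evaluable (13.3.2).
- Counts taken after another agent has started would not isolate recovery from SAR440234, so longer follow-up would not settle the criterion cleanly.

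Two further objections have some force. First, the weight of the text favors longer follow-up: ten provisions against two, with 10.5.3 worded as an obligation that reaches past leaving the trial. That makes loss less likely, but a site reading 6.8.1 or the summary would not know it. Second, a stop at new therapy can be defended because later events are harder to attribute. That is a reason to record when the new therapy began. It does not reconcile the two rules.

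**Conclusion.** The contradiction stands. The summary and Section 6.8.1 allow follow-up of open SAEs and IMP-related AEs to end at new therapy; 10.5.3 and nine other provisions do not. The visit rules in 12.7 and footnote c leave such events without a scheduled contact even where follow-up is required.

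The consequence is possible loss of outcome and resolution data for open SAEs, AESIs and related AEs. Its size cannot be estimated, because the documents do not give the share of patients who start another therapy with an event still open. The conclusion assumes only that some patients will do so and that some sites will act on 6.8.1 or the summary. It does not extend to DLT classification or the escalation decision, for which no effect is shown.

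**What to change.** Reconcile the passages so that one end point applies to safety follow-up:

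1. In the Clinical Trial Summary and Section 6.8.1, remove the new-therapy stop for open SAEs, AESIs and IMP-related AEs.
2. In the visit sentence of 12.7 and in footnote c of flow charts 1.2.2 and 1.2.4, state that new therapy ends only the disease-status visits, and that open events continue to be followed to resolution or stabilization under 10.5.3. Changing only the summary and 6.8.1 would leave the flow charts in conflict with themselves.
3. Record the start date of the new therapy with each open event, so that later data can be interpreted.

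The cost is a wording change and slightly longer safety follow-up for a few patients. Telephone contact and record review are already provided for in 6.8.1, 11.1.2 and 12.7, so no new procedure is needed. No dose or treatment rule changes.

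The SAP states that the trial ended early. If the wording can no longer be changed in time, the listings could show, for each SAE, AESI or related AE open at discontinuation, whether follow-up ended by resolution, stabilization or new therapy.

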- a **Evaluation:** Assessments should be performed prior to administration of SAR440234 (end of the previous cycle) unless otherwise indicated, at the end of the patient's participation in the trial, and at follow-up. Results should be reviewed by the Investigator prior to the administration of the next dose. If the patient is unable to attend monthly study visits, the investigator must obtain study follow up information via telephone call and record review from the patient's treating physicians.
- b End of treatment (within 30 days after the last administration of SAR440234): Obtain end of treatment assessments. If the patient does not plan to return for an EOT visit, the EOT evaluation must be performed on the day that the decision is made that the patient will not continue SAR440234.
- c **Post-study follow-up** for disease status, IMP-related AEs, and SAEs: Patients without documented disease progression at the end of a treatment visit who have not yet started treatment with another anti-cancer therapy will proceed with monthly follow-up visits until initiation of another anti-cancer therapy, disease progression, study cut-off date, or death. If the patient is unable to attend monthly study visits, the investigator must obtain study follow up information via telephone call and record review from the patient's treating physicians.
- d Day 1: Cycles run consecutively so that Day 1 of each cycle is normally 7 days after the start of the last infusion in the previous cycle.
- e Bone marrow aspiration will be performed for morphology (% of blasts) on Day 42 (±2 days) of Cycle 2 for evaluation of disease status. Subsequent bone marrow aspirates will be performed when clinically indicated, or if any of the following occurs: decreased neutrophil count Grade 4, decreased platelet count Grade 4, febrile neutropenia Grade 3 and Grade 4, anemia Grade 4 occurs with onset in >14 days before or after Day 42.
- f Flagged assessments: Cycle 2 only. Not required during Cycle 3 and subsequent cycles unless clinically indicated.
- g Blood hematology: Daily during Week 1 of Cycle 2, then weekly thereafter (on IMP administration days and on Day 42). Hemoglobin, hematocrit, white blood cell count with differential, percentage of blasts, platelet count.

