#### 12.8 POST STUDY CUT-OFF PERIOD

If a patient continues to benefit from the treatment after the second study cut-off date, the patient can continue study treatment until disease progression, unacceptable toxicity or patient request. Such patients will be followed until 30 days after the last administration of the IMP and will continue to undergo select study assessments. The following information will be collected: IMP(s) administration, IMP-related AEs, and any SAEs.

No follow-up information will be collected after these patients discontinue study treatment, with the exception of all SAEs regardless of relationship to study treatments and all IMP-related AEs still ongoing at the end of study treatment and any new treatment-related AE/SAEs occurring after the end of study treatment which will be followed until resolution/stabilization.

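### As worded, the second cut-off can fall before other late-starting Expansion patients reach their two-cycle response assessment

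*Protocol*

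**What the plan says.** The Clinical Trial Summary (Duration of study period) states: "The second cut-off date will be when the last patient in the Expansion Part will have been treated for 2 cycles". Section 6.8.1 has the same rule, with its alternative trigger and purpose: "will have been treated for 2 cycles (approximately 3 months), or has early progression, whichever occurs first, in order to assess tumor response". Neither place defines the last patient or sets a condition for the rest of the cohort.

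For patients still on treatment after that date, Section 6.8.1 says "they will only be followed for study treatment administration, SAEs, study treatment-related AEs, and reason for end of treatment". Section 12.8 is consistent with this: "The following information will be collected: IMP(s) administration, IMP-related AEs, and any SAEs". For patients off treatment without progression, Section 6.8.1 continues monthly visits "until initiation of another anti-cancer therapy, disease progression, study cut-off date, or death, whichever comes first".

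Response is read on marrow. Section 1.2.3 (footnote c) schedules an aspirate on Day 42 of Cycle 1. Section 1.2.4 (footnote e) schedules the second: "Bone marrow aspiration will be performed for morphology (% of blasts) on Day 42 (±2 days) of Cycle 2 for evaluation of disease status". Section 6.8.1 gives the cycle length: "The cycle duration is 42 days with weekly IMP administration".

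Two places point the other way. Section 1.2.4 (footnote w) has disease status collected monthly until death or new anti-neoplastic therapy, with no stop at a cut-off. Section 12.7 follows responders and stable patients to progression or new therapy.

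**The concern.** The second cut-off exists to support the Expansion response assessment, and ORR is the endpoint that carries the Simon test. Without the early-progression alternative, the rule would work: once the last patient to start has completed two cycles, everyone who started earlier has had at least as long, apart from dose delays. The alternative makes sense for the patient who progresses, who has nothing more to contribute to response. It does not make sense as a date for everyone else, because it ties their data collection to another person's event.

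The protocol sets a maturity standard for its other decision points. The interim looks at the first 17 patients after two cycles, and the first cut-off is placed so that Cycle 1 is evaluable for all patients. The final ORR cut-off has no such condition. A patient cut off before any evaluable assessment leaves the efficacy population (Section 13.3.4), and one cut off between the two marrows loses the second chance to be seen as a responder. The rejection threshold remains 11 of 37.

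**Working it through.** **1. The plan's own figure.** Inputs from Section 13.1.2 and the Clinical Trial Summary: p0 = 0.20, p1 = 0.40, stop if 3 or fewer of the first 17 respond, reject if at least 11 of 37 respond, one-sided alpha 10%, power 90%.

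P(reject | p) = sum over x = 4 to 17 of P(Bin(17, p) = x) × P(Bin(20, p) ≥ 11 − x)

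- p = 0.20: 0.0948
- p = 0.40: 0.9033

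The stated design reproduces, and a search over two-stage designs returns it as the optimal one (expected size 26.0 under the null).

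**2. Who is short of assessment at the cut-off.** Two cycles are 2 × 42 = 84 days. Let the last patient to start progress t days after first dose. A patient who started d days before that patient has been on study d + t days at the cut-off. So:

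- d < 84 − t: short of the Cycle 2 Day 42 marrow.
- d < 42 − t: also short of the Cycle 1 Day 42 marrow.

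At t = 21 these windows are 63 and 21 days before the last patient's first dose.

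**3. How many.** The documents give no accrual rate. Assuming steady accrual of r patients a month, the number short of 84 days is r × (84 − t)/30.44, and the number short of 42 days is r × (42 − t)/30.44 (zero once t reaches 42).

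| t (days) | r = 2: short of 84 / of 42 | r = 4: short of 84 / of 42 |
|---|---|---|
| 14 | 4.6 / 1.8 | 9.2 / 3.7 |
| 21 | 4.1 / 1.4 | 8.3 / 2.8 |
| 28 | 3.7 / 0.9 | 7.4 / 1.8 |
| 42 | 2.8 / 0 | 5.5 / 0 |

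At t = 21, then, about 4 to 8 patients miss the second marrow, and about 1 to 3 of them miss both.

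**4. Effect on the test.** All affected patients are in Stage 2. The threshold is held at 11 and an unseen response counts as none. A fully missed patient has response probability 0; a half-missed patient (first marrow seen, second not) is assumed to have probability 0.5 × p. The calculation in step 1 is repeated with these probabilities for the affected patients.

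| Affected patients | Power (p = 0.40) | Alpha (p = 0.20) |
|---|---|---|
| None | 0.903 | 0.095 |
| 1 fully, 3 half missed | 0.857 | 0.065 |
| 3 fully, 5 half missed | 0.765 | 0.037 |
| 4 fully missed (bound) | 0.820 | 0.049 |
| 6 fully missed (bound) | 0.749 | 0.032 |
| 8 fully missed (bound) | 0.655 | 0.020 |

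The second and third rows match t = 21 at 2 and 4 patients a month.

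**The case against.** The strongest reply is that the wording need not mean the last patient to start. It could mean the last patient to reach either two cycles or progression, and then there is no gap. The purpose of the cut-off and the maturity rules for the interim and the first cut-off favour that intent. This stands as a point about intent, but the text does not say it, and a cut-off date should not depend on how an undefined term is read.

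A reader might also infer that disease status simply stops being collected. The documents do not support that. Section 1.2.4 (footnote w) and Section 12.7 imply continued collection, Section 12.8 keeps some study assessments going, and the Cycle 2 marrow has no exception for the cut-off. Against them stand the restriction to named items in Section 6.8.1, the data list in Section 12.8 and the visits that end at the cut-off. This is a contradiction to resolve, not a settled absence of response data.

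Nor do the documents support taking 0.66 as the expected power. It requires that none of the eight affected patients had been seen to respond by Cycle 1 Day 42, yet at t = 21 about two-thirds of them have passed that marrow. Finally, the documents give no figure for how likely early progression of the last patient is. Progression on Day 14 or 21 is possible, but is not shown to be typical.

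**Conclusion.** The point holds as a defect in the stated rule. On a literal reading, one patient's early progression can set the second cut-off before other late-starting Expansion patients have had their Cycle 2 Day 42 marrow, and the protocol contradicts itself on whether their response is still recorded. The Simon design itself is correct.

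Under the assumptions shown (2 to 4 patients a month, progression on Day 21, half of responses visible at the first marrow), power falls from 0.903 to about 0.86 or 0.77. The range 0.82 to 0.66 for 4 to 8 patients is a worst-case bound. Alpha falls as well, so the error runs toward missing an active drug and not toward a false claim. Accrual, timing of progression and the share of late responses are all assumed.

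A reader might infer that the trial's reported results are affected. They are not: SAP Sections 4.3, 4.4 and 4.9 drop the efficacy endpoints and the interim because of early termination, so no ORR test will use this cut-off.

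**What to change.** In Section 6.8.1 and the Clinical Trial Summary, replace the trigger with wording such as: *The second cut-off is the date by which every Expansion patient has completed the Cycle 2 Day 42 disease assessment, or has permanently discontinued treatment, progressed or died; where a patient discontinues, the Day 42 evaluation is done at that time where possible.* State that disease status is collected for each patient at least until that point. Then align Section 1.2.4 (footnote w), the follow-up rule in Section 6.8.1, Section 12.7 and Section 12.8, so that they agree on what is collected after the cut-off.

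The cost is one sentence in two places plus the alignment. The cut-off moves later by up to about 84 days minus the last patient's time to progression (63 days in the Day 21 example), plus any cycle delays. No patients or procedures are added, because the Cycle 2 marrow is already scheduled.
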